# 7.3 Quality Assurance Audit

Study sites, the study database and study documentation may be subject to Quality Assurance audit during the course of the study by the Sponsor or on behalf of the Sponsor. In addition, inspections may be conducted by regulatory bodies at their discretion.

# 8.0 STATISTICS

# 8.1 Determination of Sample Size

The sample size is based on being able to claim superiority of V565 over placebo; the primary endpoint is defined as a response rate, based on CDAI reduction/remission and CRP or FCP results.

A subgroup of subjects will be assessed by endoscopy for changes in overall mucosal appearance and changes in SES-CD. However, the study is not powered to show a difference in these endpoint.

# 8.2 Statistical Methods

The default summary statistics for continuous variables include number of contributing observations [n], mean, standard deviation (SD), median, minimum, and maximum.

For categorical variables, the number and percentage (the percentage of subjects in each category relative to the total number of subjects in the relevant analysis population or relative to the total number of subjects in the relevant analysis population, with assessments available [where appropriate]) in each category will be the default summary presentation.

Unless otherwise specified, "Baseline" is defined as the last observed value of the parameter of interest prior to the first intake of study medication (this includes unscheduled visits). For numerical variables, change from Baseline will be calculated as the difference between the value of interest and the corresponding baseline value.

Unless otherwise specified, all formal statistical tests will be two-sided at the 5% significance level. Point estimates of treatment differences will be accompanied with two-sided 95% confidence intervals (CIs) where applicable.

In the case of normality assumption violations, appropriate non-parametric methods will be used for analysis.

All data will be presented in by-subject listings.

The statistical analysis will be performed using SAS® Version 9.2 or higher.

### 8.2.1 Primary Efficacy Analysis

The primary clinical efficacy endpoint of the study is the proportion of subjects at Day 42 that have both CDAI  $\geq$ 70-point reduction from Baseline or CDAI <150, *and* a reduction of  $\geq$ 40% from the baseline value of CRP or FCP.

### 8.2.2 Secondary Efficacy Analyses

The secondary endpoints below will be analysed using the same model as used in the primary endpoint analysis.

- Proportion of subjects achieving a ≥100-point reduction in CDAI score and a concomitant reduction of 50% in CRP or FCP at Day 42
- Proportion of subjects achieving a  $\geq$ 70-point reduction in CDAI score at Day 42
- Proportion of subjects achieving a  $\geq$ 100-point reduction in CDAI score at Day 42
- Proportion of subjects achieving a CDAI score of <150 CDAI at Day 42

For the PRO-2 score assessments, the changes in total scores from Baseline to Day 14 and Day 42 will be analysed using a Mixed Model for Repeated Measures (MMRM) with treatment as the fixed effect, prior anti-TNF $\alpha$  and baseline scores as covariates.

### 8.2.3 Exploratory Analyses

The exploratory endpoint evaluating the proportion of subjects achieving CRP (or FCP) levels within normal limits at Day 14 and Day 42 will be summarised using frequency and percentage.

The endpoints evaluating changes in CDAI score over time and changes in CRP (or FCP) results over time will be summarised using descriptive statistics.

The anti-V565 antibody responses will be summarised and listed for the safety (SAF) population.

In the exploratory endoscopy substudy, changes in the central reader's overall assessment and changes in SES-CD from Baseline to Day 42 will be summarised using descriptive statistics. Summary statistics presentation will be separated for subjects with ileum and colon involvement and for subjects with only ileal mucosal lesions.

Any additional analyses or data presentation details will be described in the SAP.

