In an exploratory endoscopy substudy, subjects with more severe disease at the Visit 2 ileocolonoscopy (a SES-CD  $\geq$ 7, if ileum and colon are involved or  $\geq$ 4 if only the ileum is involved) will undergo a second ileocolonoscopy at the end of treatment (Day 42) to evaluate changes in the mucosa.

Pharmacokinetic (PK) evaluations will be based on concentrations of V565 measured in serum and urine. Safety will be assessed through evaluations of adverse events (AEs), clinical laboratory results, vital signs, physical examinations, electrocardiograms (ECGs) and concomitant medications.

Planned number of subjects:	Approximately 126 randomised to receive study drug in a
3	2:1 active:placebo ratio (84:42)
	Approximately 114 to complete (76:38) based on an estimated dropout
	rate of 10% during treatment

Diagnosis and main criteria for inclusion:	This study will enrol adult subjects with active CD. The main criteria for inclusion are:
	
 
History of CD (confirmed by ileocolonoscopy) of at least three months duration prior to Visit 1
 
CDAI score of ≥220 to ≤450 during Screening
 
CRP ≥5 mg/L (or, if CRP is normal, FCP ≥250 µg/g) at Screening
 
Active CD of ileum and/or colon as determined by the baseline ileocolonoscopy
 
Female subjects must not be pregnant and male and female subjects must agree to use effective contraception throughout the study and for 90 days after the last dose of study drug.
 
Subject must have failed or experienced intolerance to at least one of the following: aminosalicylates, corticosteroids; immunosuppressants (e.g., azathioprine [AZA], 6-mercaptopurine [6-MP], or methotrexate [MTX]).
 

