#### **3.1.2** Secondary Objectives

Secondary objectives are:

- To further characterise the efficacy of V565 in subjects with active CD assessed by changes in CDAI scores and/or inflammatory markers
- To assess the effects of V565 based on changes in Abdominal Pain and Stool Frequency Instrument (PRO-2) scores
- To assess safety and tolerability of V565

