# 5.6 Method of Assigning Subjects to Treatment Group

Once the subject provides an informed consent and meets inclusion and exclusion criteria, the study site will request the study drug assignment using the Interactive Web Activated Response System (IWRS). Approximately 126 subjects will be randomised in a 2:1 ratio (84 subjects in the V565 arm and 42 subjects in the placebo arm). Randomisation will be stratified to ensure treatment groups have similar rates of prior anti-TNF $\alpha$  therapy.

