### **15.3.3.** ANALYSIS OF EXPLORATORY VARIABLES

- 15.3.3.1. The proportion of subjects achieving CRP (or FCP) levels within protocol defined normal limits at Day 14 and Day 42
- will be summarised using frequency and percentage and listed by subject for the ITT population
- 15.3.3.2. The endpoints evaluating changes in CDAI score over time and changes in CRP (or FCP) results over time
- will be summarised using descriptive statistics and listed by subject for the ITT population

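### Full-scale CDAI and CRP/FCP changes get no treatment estimate: total CDAI is tested only at cut points, although a supportive full-scale analysis would need no new data

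*Protocol*

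**What the plan says.** One secondary objective (Protocol 3.1.2, repeated in SAP 2.2) is: "To further characterise the efficacy of V565 in subjects with active CD assessed by changes in CDAI scores and/or inflammatory markers".

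The endpoints that receive a between-arm logistic model (Protocol 8.2.1 and 8.2.2) are:

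- the primary composite: CDAI fall of ≥70 or score <150, together with a ≥40% fall in CRP or FCP;
- CDAI fall of ≥100 together with a 50% fall in CRP or FCP;
- CDAI fall of ≥70;
- CDAI fall of ≥100;
- CDAI <150.

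For the same measures on their full scale, Protocol 8.2.3 says "The endpoints evaluating changes in CDAI score over time and changes in CRP (or FCP) results over time will be summarised using descriptive statistics". SAP 15.3.3.2 says they "will be summarised using descriptive statistics and listed by subject for the ITT population". Protocol 8.2 and SAP 6 define those statistics as n, mean, SD, median, minimum and maximum.

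PRO-2 is treated differently. Its change from baseline to Day 14 and Day 42 "will be analysed using a Mixed Model for Repeated Measures (MMRM" with baseline and prior anti-TNF therapy as covariates (Protocol 8.2.2). Protocol 6.1.4 takes PRO-2 from the stool and abdominal-pain entries of the CDAI diary.

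**The concern.** Each CDAI cut reduces a continuous score to yes or no. The three single cuts and the two composites overlap heavily, so they add little independent information to one another. CDAI and the qualifying marker are already collected at baseline, Day 14 and Day 42, yet neither gets an estimated treatment difference, a confidence interval or a baseline adjustment on its own scale. Two CDAI items get such an estimate through PRO-2, while the eight-item index behind the primary does not.

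This matters in a proof-of-concept trial with 42 placebo subjects. If the responder result is borderline, the tested endpoints cannot readily separate no effect from an effect lost at the threshold. A CDAI or marker contrast added after unblinding would be post hoc.

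**Working it through.** **Inputs from the documents.** Level: "all formal statistical tests will be two-sided at the 5% significance level" (Protocol 8.2). Size: "Approximately 126 subjects will be randomised in a 2:1 ratio (84 subjects in the V565 arm and 42 subjects in the placebo arm" (Protocol 5.6). Completers: "Approximately 114 to complete (76:38) based on an estimated dropout" with "rate of 10% during treatment" (Synopsis).

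**The plan's own figure.** 126 × 0.9 = 113.4, in line with 114. In the other direction, 114 / 0.9 = 126.7, or 127, within rounding of 126. Only this dropout step can be checked, because the public text shows no power, response rates, SD or CDAI effect. All rates and SDs below are therefore assumptions.

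**Which CDAI cut the primary uses.** SAP 6.2 takes the screening CDAI as baseline, and eligibility requires at least 220. A score below 150 then means a fall of more than 220 − 150 = 70, so in eligible subjects the <150 limb adds no responders to the ≥70 limb.

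**Cut versus full scale, CDAI alone.** Assume a normal CDAI change with equal SD in both arms and a drug effect that shifts the distribution.

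1. Cut: power = Φ[(p1 − p0 − 1.96·SE0)/SE1], with SE0 = √[p̄(1 − p̄)(1/n0 + 1/n1)] and SE1 = √[p0(1 − p0)/n0 + p1(1 − p1)/n1]. Solve for the p1 that gives a chosen power.
2. Convert to a standardised shift: d = Φ⁻¹(p1) − Φ⁻¹(p0).
3. Full scale: two-sample t-test, noncentrality d·√[n0·n1/(n0 + n1)]. At 84:42 the root is √28 = 5.29.

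Example with p0 = 0.30 and p1 = 0.560:

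- p̄ = (42 × 0.30 + 84 × 0.56)/126 = 0.473, SE0 = 0.0944, SE1 = 0.0891.
- Cut: (0.26 − 1.96 × 0.0944)/0.0891 = 0.84, power 80%.
- d = 0.151 + 0.524 = 0.675, noncentrality 3.57, full-scale power 94.3%.

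Full-scale power (%) at 84:42:

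| Cut power | p0 0.15 | 0.20 | 0.30 | 0.40 | 0.50 | Gain (points) |
|---|---|---|---|---|---|---|
| 50 | 81.8 | 77.2 | 71.5 | 69.1 | 68.9 | 18.9 to 31.8 |
| 60 | 89.1 | 85.5 | 81.0 | 79.1 | 79.3 | 19.1 to 29.1 |
| 70 | 94.1 | 91.7 | 88.6 | 87.4 | 87.9 | 17.4 to 24.1 |
| 80 | 97.4 | 96.1 | 94.3 | 93.8 | 94.4 | 13.8 to 17.4 |
| 90 | 99.3 | 98.9 | 98.2 | 98.2 | 98.6 | 8.2 to 9.3 |

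At 76:38 the gains are the same to within about 0.2 points. Over cut power of 50% to 80% the gain is 13.8 to 31.8 points.

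The top of that range depends on the pooled null variance. With SE1 in place of SE0, the worst case (p0 = 0.15, 50% power) has p1 = 0.296, d = 0.499 and full-scale power 74.6%. The gain there is 24.6 points, and over the same grid it is about 13 to 25.

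**Cross-check with baseline-adjusted models.** Simulation used 2,000 runs per case, logistic regression on each cut against ANCOVA on CDAI change, both adjusted for baseline CDAI, with SD 80 to 100 and true difference 30 to 70. The gain was about 10 to 23 points for ≥70, 12 to 28 for ≥100 and 20 to 51 for <150. For example, with difference 50, SD 100 and 76:38, power was 52.7% (≥70), 50.5% (≥100), 38.6% (<150) and 71.4% (ANCOVA).

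**Where the gain is small.** Suppose only 35% of active subjects benefit, by 120 points, with SD 70 and a placebo mean fall of 30, at 76:38. The ≥100 cut then has about 68% power and the t-test about 72%, a gain of about 4 points. For ≥70 the gain stays near 15 or above. Over a wider shift grid (placebo rate 10% to 50%, rate difference 10 to 30 points) the gain runs from about 3 to 40 points.

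**The case against.** Change over time in CDAI and CRP/FCP is listed as an exploratory objective (Protocol 3.1.4), and descriptive analysis of exploratory endpoints is a normal choice. The secondary objective has its own named endpoints. PRO-2 already gives part of the CDAI signal a full-scale test. The by-arm means, SDs and counts would let a reader compute a crude difference and interval. The public SAP is also incomplete: its contents list an analysis section for secondary variables and Mann-Whitney code that cannot be read.

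Much of this stands. The plan does not contradict itself, and it is not without any full-scale efficacy test. But SAP 15.3.3.2 is visible and explicit, and the non-parametric fallback in SAP 6 points to section 15.2.3, which falls under secondary efficacy. Nothing visible extends a test to CDAI or marker change. A crude difference computed from summary tables would be neither baseline-adjusted nor prespecified.

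A reader might also infer that the biomarker change is taken only in raw units, at odds with the proportional response rule. The documents do not support that: SAP 6.7, to which SAP 15.3.1.3 refers, defines percent change as well as change. It is only unclear which formula applies.

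**Conclusion.** The point holds as a missed gain in precision. It is not an error in the primary analysis. For CDAI alone, under a normal, equal-SD shift, full-scale analysis gains about 14 to 32 points of power over a cut with 50% to 80% power at placebo rates of 15% to 50%. The gain is about 8 to 9 points at 90% cut power, and about 4 for the ≥100 cut in the subset-response scenario.

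Three stronger readings are tempting but unsupported:

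- **That this trial gives up 14 to 32 points.** The range is conditional on assumed rates and power. It is not a bound, and baseline-adjusted models gave about 10 to 23 for ≥70.
- **That the same loss applies to CRP/FCP.** No marker-only power was computed. Protocol 6.1.3 limits on-treatment FCP to subjects who qualified on it, and SAP 3.3 regards CRP in those subjects as uninformative. Separate tests of each marker would therefore use only part of the sample.
- **That the primary loses this much.** The composite also requires a marker fall. Comparing it with a CDAI-only test compares different hypotheses, and its planned power is not public.

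**What to change.** Leave the primary responder endpoint unchanged. Before unblinding, amend Protocol 8.2.3 and SAP 15.3.3.2 to prespecify two supportive ITT analyses:

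1. **CDAI change.** MMRM on Day 14 and Day 42 with treatment, visit, treatment-by-visit, prior anti-TNF therapy and baseline CDAI. Report the Day 42 adjusted mean difference with 95% CI.
2. **Qualifying marker.** The same model on log(Day x / baseline) of the marker on which each subject qualified, adjusting for marker type and for log baseline within marker type in place of baseline CDAI. Report the Day 42 ratio of geometric means with 95% CI. This pools CRP and FCP qualifiers as the responder definition in SAP 15.1.1 does, and its ratio scale matches the 40% rule.

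Label both as supportive and outside the primary claim.

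The cost is wording and two model fits, with no new data, visits or subjects. The small downside is two more unadjusted comparisons in a plan that makes no multiplicity adjustment (SAP 7.4).

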### 8.2.4 Pharmacokinetic Analysis

Samples for analysis of concentrations of study drug will be collected as specified on the Schedule of Events (). Individual PK blood sample collection dates/times, urine sample collection dates/times/sample volume and the associated V565 concentrations will be listed.

Serum V565 concentrations will be summarised using descriptive statistics by planned sampling time.

The amount of V565 excreted in each urine collection will be determined as V565 concentration  $\times$  urine volume of the urine sample and listed for each subject by visit.

### 8.2.5 Safety Analyses

All safety data will be provided in by-subject listings.

### 8.2.5.1 Adverse Events

Treatment-emergent Adverse Event: A TEAE is defined as:

- A new event that occurs during or after treatment with study drug or
- Any event present at Baseline that worsens in either intensity or frequency after exposure to study drug.

Only TEAEs will be summarised.

The number and percentage of subjects experiencing TEAEs and serious TEAEs will be summarised by treatment group, and by MedDRA System Organ Class (SOC) and Preferred Term. The TEAEs will also be summarised by maximum severity and relationship to study medication in addition to SOC, Preferred Term and treatment group. Summaries will also be presented for serious TEAEs and for TEAEs leading to permanent discontinuation.

Medical history will be coded using the MedDRA latest version and listed for all subjects.

### 8.2.5.2 Safety Laboratory Tests

The results of safety laboratory tests will be summarised for each laboratory parameter and planned visit time point.

Continuous laboratory parameters will be summarised by visit time point using the number of subjects with non-missing data, mean, SD, median, minimum and maximum. Actual values as well as changes from Baseline will be summarised.

Categorical parameters will be summarised by the number and percentage of subjects within each category, relative to the total number of subjects in the SAF, with data available. In the event of missing test results, a "missing" category showing the number of subjects with missing test results at each level of summarisation will be presented.

Shift tables for specific time points versus baseline status will be presented for both continuous (categorised in accordance with study-specific reference ranges as Low, Normal, High) and categorical (using appropriate categories such as Normal, Abnormal) laboratory parameters. "Time point" in these tables may be either a specific visit, a final study visit or the entire study duration on-treatment.

# 8.2.5.3 Vital Signs and 12-lead ECG

Vital signs statistics will be presented in a similar way to the laboratory variables.

All ECG data results (normal/abnormal) will be summarised using frequency counts and percentages. Clinically significant abnormalities will be presented in by-subject listings.

### 8.2.5.4 Physical Examinations

Physical examination results will be summarised using frequency tables for normal/abnormal results per visits.

### 8.2.5.5 Concomitant Medications

All medications will be coded using the WHO Drug Dictionary and ATC system. Each medication will be classified as prior medication if it is stopped prior to the first dose of study medication, or as concomitant medication if it is ongoing at the time of the first dose or is started after the first dose of study medication. Prior and concomitant medications (other than permitted medications for the treatment of CD) will be summarised by treatment group by ATC level 2 categories and preferred name.

Permitted medications for the treatment of CD will be summarised separately.

### 8.2.6 Data To Be Analysed

All details regarding the statistical analysis and the preparation of tables, listings and figures will be described in the SAP prepared by and approved by the Sponsor before database lock.

### 8.2.7 Analysis Populations

Intent-to-Treat (ITT) population: The ITT population will include all randomised subjects. In this population, treatment will be assigned based upon the treatment arm to which subjects were randomised regardless of which treatment they actually received.

Per Protocol population (PP): The PP population will include all subjects who do not have major protocol violations that would affect the evaluation of the primary efficacy endpoint.

Safety population (SAF): The SAF population will include all randomised subjects who receive at least one dose of study drug. In this population, treatment will be assigned based upon the treatment subjects actually received, regardless of the treatment to which they were randomised.

Pharmacokinetic population (PK): The PK population will include all subjects in the SAF population who receive at least one dose of study drug and who have at least one post dose sample of serum and urine who do not have events or protocol deviations with the potential to affect PK concentrations.

### 8.2.8 Missing Data

Missing data handling and possible sensitivity analysis will be described in the SAP.

### 8.2.9 Subgroup Analysis

No subgroup analyses are planned.

### 8.3 Interim Analyses

No interim analysis for efficacy or safety is planned.

# 9.0 ETHICS

# 9.1 Institutional Review Board or Independent Ethics Committee

An ethics committee should approve the final protocol, including the final version of the ICF and any other written information and/or materials to be provided to the subjects. The Investigator will provide the Sponsor or with documentation of IRB/IEC approval of the protocol and informed consent before the study may begin at the study site(s). The Investigator should submit the written approval to Sponsor or representative before enrolment of any subject into the study.

Sponsor or representative should approve any modifications to the ICF that are needed to meet local requirements.

The Investigator will supply documentation to the Sponsor or of required IRB/IEC's annual renewal of the protocol, and any approvals of revisions to the informed consent document or amendments to the protocol.

The Investigator will promptly report any new information that may adversely affect the safety of subjects or the conduct of the study to the IRB/IEC. Similarly, the Investigator will submit written summaries of the study status to the IRB/IEC annually, or more frequently if requested by the IRB/IEC. Upon completion of the study, the Investigator will provide the IRB/IEC with a brief report of the outcome of the study, if required.

Sponsor or representative will provide Regulatory Authorities, ethics committees and Investigators with safety updates/reports according to local requirements, including SUSARs, where relevant.

Each Investigator is responsible for providing the IRB/IEC with reports of any serious and unexpected adverse drug reactions from any other study conducted with the study drug. The Sponsor or representative will provide this information to the Investigator so that he/she can meet these reporting requirements.

# 9.2 Ethical Conduct of the Study

This study will be conducted, and the informed consent will be obtained, according to the ethical principles stated in the Declaration of Helsinki (64th WMA General Assembly, Fortaleza, Brazil, October 2013), the applicable guidelines for good clinical practice (GCP) (CPMP/ICH/135/95), or the applicable drug and data protection laws and regulations of the countries where the study will be conducted.

GCP is an international ethical and scientific quality standard for designing, conducting, recording, and reporting studies that involve the participation of human subjects. The study will be conducted in compliance with GCP and the applicable national regulations to assure

that the rights, safety and wellbeing of the participating study subjects are protected consistent with the ethical principles that have their origin in the Declaration of Helsinki.

